6) **Study-Wide Recruitment Methods***

N/A.

7) **Study Timelines***

Patients will participate for 3 weeks in total. Enrollment will be complete by 2 years and the primary analyses will be completed in 2.5 years duration.

8) **Study Endpoints***

The primary endpoint of the study is the resolution of follicular conjunctivitis and symptomatic improvement in the viral conjunctivitis arm.

9) **Procedures Involved***

Patients will be diagnosed by clinical exam in the Bascom Palmer Emergency Department. Those meeting inclusion criteria will be randomized to Avenova® spray vs artificial tears (placebo), to be used in the affected eye four times a day for two weeks duration in total. Samples of the tears from the ocular surface and conjunctiva will be obtained through cotton swabs from the patient's initial visit and daily to every-other-day through 1 week, and finally at week 2 (e.g. Day 0, 1, 2, 3, 4, 5, 6, 7, and 14 +/- 1 day). These samples will be obtained in both groups (Avenova® spray and artificial tears). Collected samples will be sent to the Bascom Palmer Microbiology laboratory for PCR evaluation and microbiology evaluation and then promptly disposed of. Patients will return once every week for 3 weeks duration in order to assess for resolution of follicular conjunctivitis and symptomatic relief based off the subjective scoring guidelines (see supplemental material) as well as physical exam findings (lymphadenopathy, follicular conjunctivitis, injection, discharge, subepithelial infiltrates, conjunctival pseudomembranes) *See Objective Questionnaire*. Patients will be questioned about adverse effect to treatment each visit and be assessed for surrounding periorbital dermatitis. However, Avenova® has a wide range of indications for use and is approved by the FDA as a medical device for use on the skin.

10) **Data Management***

Viral conjunctivitis

POWER ANALYSIS:

%spontaneous resolution in 7 days: 20%

%Resolution with treatment: 50%

N=39 for each treatment group for power of 80%

Data will include medical record number, diagnosis, type of therapy, commentary on improvement/worsening of signs and symptoms. It will also include adverse events.

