Research data can only be accessed by clinicians (whose names have been added to the IRB) in direct care of the patient or those listed on the IRB. All identifiable data will be stored on a locked and encrypted USB drive and will be de-identified of personal identifying information at the conclusion of the study once all data is analyzed, which will again be stored on a locked and encrypted USB drive. The investigatory team will assign subject identifiers and study records will be locked in the office of [name] on the [name] of the Bascom Palmer Eye Institute located at [name].

11) **Provisions to Monitor the Data to Ensure the Safety of Subjects***

Subjects will return for follow up appointments at weekly intervals for three weeks total. It is safe to monitor these patients at these intervals as these viral infections are self-limiting and often resolve with time. As there is currently no treatment for these infections, observation and symptomatic management is standard of practice.

Co-investigators on the study will assess patients at each of the follow-up visits for any side effects (listed in the informed consent) to the assigned medical treatment and document this in the electronic medical health record. Patients will be given the telephone number of a principle investigator if they believe they are having a significant side effect or may also present at the 24 hour emergency department at the Bascom Palmer Eye Institute. If there are noted adverse reactions to the device, participation in the study will be terminated for that individual patient. Data will be analyzed by members of the IRB team at weekly intervals, and if during the study, greater than 20% of patients are observed to have an adverse reaction to the spray, the study will be terminated prematurely.

12) **Withdrawal of Subjects***

Patients will be withdrawn from the study if the physician deems their symptoms to be clinically related to administration of the device. Patients may withdraw voluntarily from the study at any time, but will be continued to be followed for the duration of the study. Non-compliant patients (those who do not take the study device) will be allowed to continue in their respective groups (Avenova® versus artificial tears) for the duration of the study.

13) **Risks to Subjects***

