Bascom Palmer Eye Institute is an ophthalmic hospital with a 24 hour emergency department specializing in ophthalmic disease. The institute receives a wide referral base including all of Florida and the surrounding sites, as well as numerous international referrals due to its prominence in the field of ophthalmology. This institute is staffed with residents, fellows and attending’s, all specialized only in the field of ophthalmology. Each week, the emergency department diagnoses at least 10 cases of viral conjunctivitis. If half of these cases agree to participate in the study, there will be adequate number of patients to power the study.

Before the start of the study, all participating members will be informed of the study, as well as possible risks, benefits and their role within the study.

We plan to devote 24 months to collecting patients as well as the statistical analysis for the study.

18) Recruitment Methods

Patients will be recruited from the Bascom Palmer Eye institute emergency department as a referral. Potential subjects are those identified as being infected with viral conjunctivitis by the ophthalmologist. There will be no advertisements for this study and no payment will be offered to participants of the study. If the patient consents to the study, he/she will be randomly assigned to Avenova® vs artificial tears through a randomization computer program.

19) Confidentiality

Identifiable data will be stored on a locked and encrypted USB drive to be locked in the office of [name] on the [name] of the Bascom Palmer Eye Institute located at [name]. This data will be de-identified of personal identifying information at the conclusion of the study. The investigatory team will assign subject identifiers and study records will only be accessed by the study coordinators.

20) Provisions to Protect the Privacy Interests of Subjects

To limit intrusiveness to patients, data will only be collected during clinic follow-up (once every week for three weeks). Patients will receive a subjective questionnaire (see supplemental material) each visit to ensure consistency between patients and between visits. The research team will then review the data collected through these questionnaires for analysis.

21) Compensation for Research-Related Injury

Patients will not be compensated for research related injuries. This will be written in the consent and described to the patient before participation in the study.

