22) Economic Burden to Subjects

The device will be provided free of cost to patients as provided by Novabay. Also, there is no cost to participants for the collection of tears via the use of cotton swab.

23) Consent Process

Consent will be obtained during an Emergency Room visit by the physician and will follow the SOP: Informed Consent Process for Research (HRP-090). The informed consent will occur that same visit to the ER; if the patient decides that he/she does not want to participate, he/she will be unable to participate at a later visit. Each visit, the patient will be asked and have the option to leave the study.

Non-English Speaking Subjects

- Spanish will be used to obtain consent in those who prefer the Spanish language—translation will be offered if needed with consent offered in the Spanish language.

24) **Process to Document Consent in Writing**

Eligible subjects will be informed of the nature, risks, and benefits of the study and informed that they are not required to participate. If interested in participating, they will be given the consent form to read, asked if they have any questions or need further explanations, and will have the option of taking the consent form home to have more time to decide about participating.

The consent process will be obtained by one of the research team members whose name and signature will be mentioned in the consent form. The details of the study will be explained to the prospective subjects.

25) **Drugs or Devices**

The device will be stored, handled and dispensed by the Bascom Palmer Pharmacy and the designated IRB study team members. The device will be administered by the patient. Avenova® has received FDA approval as a 510(k) medical device with a wide range of indications including for use on the skin surface. Note: although Novabay has been described as a funding source, only Avenova® will be provided, no direct funding will be provided.

References

2. Debabov D, Noorbakhsh C, Wang L, et al. Avenova™ with Neutrox™ (pure 0.01% HOCl) compared with OTC product (0.02% HOCl). NovaBay Pharmaceuticals, Inc., Emeryville, California, USA.

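### No masking or allocation concealment is described for a primary endpoint that rests on judgement, and the serial PCR swabs feed no stated endpoint

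*Combined protocol and SAP*

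**What the plan says.** **Arms and allocation.** Section 9: "Those meeting inclusion criteria will be randomized to Avenova® spray vs artificial tears (placebo". Section 18 adds that after consent "he/she will be randomly assigned to Avenova® vs artificial tears through a randomization computer program". Neither says who sees the result or when, or whether the two products look alike.

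**Primary endpoint.** Section 8: "The primary endpoint of the study is the resolution of follicular conjunctivitis and symptomatic improvement in the viral conjunctivitis arm". Section 9 measures the symptom part as "symptomatic relief based off the subjective scoring guidelines" and the signs by physical examination at weekly visits. The scoring sheets are supplements that were not supplied.

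**Who may know the arm.**
- Section 25: "The device will be stored, handled and dispensed by the Bascom Palmer Pharmacy and the designated IRB study team members".
- Section 10: "Data will include medical record number, diagnosis, type of therapy, commentary on improvement/worsening of signs and symptoms". It opens research data to listed clinicians in direct care and to others on the IRB list. Section 19 restricts study records to the coordinators alone.
- Section 11: "Co-investigators on the study will assess patients at each of the follow-up visits for any side effects". It ends participation for a patient who reacts to the device, and stops the study if more than 20% react to the spray. Section 12 withdraws patients whose symptoms the physician attributes to the device.
- Section 9: "Patients will be questioned about adverse effect to treatment each visit and be assessed for surrounding periorbital dermatitis".

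**Swabs.** Section 9 plans swabs in both groups on up to nine days (Days 0 to 7 and Day 14) for PCR and microbiology. Section 4 uses PCR to confirm the diagnosis. PCR is not in Section 8 or in the Section 10 data list. Section 20 confines data collection to the weekly visits.

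**The concern.** Symptom scores can shift with what the patient expects, and the grading of follicles can shift with what the examiner expects. Section 14 shows that benefit is hoped for. Nothing in the plan stops the person who dispensed, or who can see the therapy field, from grading the eye. If the enrolling physician can foresee the next allocation, the groups may also differ at entry.

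The result at stake is the primary comparison: a significant difference could come from assessment and not from the product. PCR is the planned measurement least open to expectation. With no metric, time point or test fixed for it, a PCR comparison offered in support could be chosen once the data are known.

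**Working it through.** **1. The plan's own figure.** Section 10 gives 20% against 50% resolution and 39 per group for 80% power. Two-sided 0.05 and 1:1 allocation are my assumptions, because the plan states neither. With mean rate 0.35:

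n = [1.96 × √(2 × 0.35 × 0.65) + 0.842 × √(0.20 × 0.80 + 0.50 × 0.50)]² / 0.30² = 38.5, so 39.

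The figure reproduces. Masking would not change it.

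**2. What a lean would do.** Assumptions: true resolution 20% in both arms; apparent resolution in the Avenova arm is 20% plus a lean; the primary is one binary outcome, as in Section 10; Pearson test (the plan names none). Sizes are 39/39 (Section 10) and 63/62 (the 125 of Section 5, split evenly). For each pair of counts a (Avenova) and c (tears), with pooled proportion p:

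z = (a/n₁ − c/n₂) / √[p(1 − p)(1/n₁ + 1/n₂)]

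The binomial probabilities are summed over all pairs with z ≥ 1.96.

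| Assumed lean | 39/39 | 63/62 |
|---|---|---|
| none | 0.026 | 0.026 |
| 3 points | 0.051 | 0.062 |
| 5 points | 0.077 | 0.099 |
| 10 points | 0.177 | 0.251 |

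A 3-point lean about doubles the nominal 2.5%. A larger trial makes a given lean more likely to reach significance.

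**3. Power of a Day 7 PCR endpoint.** Same method, with an assumed tears rate of 20, 30, 40 or 50% PCR-negative and a 30-point gain. A missing swab counts as not negative, so 20% loss multiplies that arm's rate by 0.8. With loss in the Avenova arm only, 20% against 50% becomes 20% against 40%, and 50% against 80% becomes 50% against 64%.

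| Loss of Day 7 swabs | 39/39 | 63/62 |
|---|---|---|
| none | 0.78-0.81 | 0.93-0.95 |
| 20% in both arms | 0.58-0.68 | 0.77-0.86 |
| 20% in Avenova only | 0.24-0.50 | 0.35-0.69 |

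The third row matters because Section 11 ends participation for reactions to the device, while Section 13 foresees no risk in the tears arm. Loss could therefore be one-sided. These figures come before any loss of patients who are PCR-negative at Day 0.

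**4. Schedule.** Daily sampling gives a Day 7 swab. Every-other-day sampling gives Days 0, 2, 4 and 6. A window of one day either side of Day 7 covers both. The one-day tolerance written in Section 9 may apply to Day 14 only.

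**The case against.** **On masking.** Calling the tears a placebo may signal an intent to mask, a computer program may well conceal assignments, and the supplements might say more. Assessing side effects of the assigned treatment does not require knowing which treatment it was. Read literally, Section 19 would keep graders away from the therapy field. All of this stands. A reader might infer that the trial is open-label, that examiners know the arm, or that allocation is predictable. The documents do not show any of these; they are silent, and they leave routes to the arm open.

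**On size.** The leans are assumed and have no basis in the documents. That also stands: 18-25% is not an estimate of this trial's error rate.

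**On PCR.** The objective concerns signs and symptoms, so a clinical primary fits it, and not every measurement must be an endpoint. The swabs have a diagnostic use and also go for microbiology, and sampling days in both groups are laid down. A reader might infer that the swabs are purposeless, but the documents do not support that. What remains is narrower: confirming the diagnosis can explain the Day 0 sample but not the later ones, and no analysis of those is specified. Nor would a PCR endpoint repair bias in the primary. It is separate, supportive advice.

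**Conclusion.** The point holds. The plan describes neither masking nor concealment. It allows study-team dispensing and clinician access to the therapy field, and it rests its primary endpoint on two judged components. Followed as written, this leaves the primary open to bias, so it is more than a missing detail.

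The direction and size of any bias are unknown. The false-positive figures are conditional on the assumed leans, the 20% rate in both arms and the assumed test.

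The withdrawal and stopping rules in Sections 11 and 12 refer only to the device or the spray, so applying them appears to need knowledge of the arm. Any masking text has to deal with that.

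The absence of a PCR endpoint is a lesser, separate point. Its power depends heavily on whether swabs are lost equally, and the 20% loss is an assumption. Sections 10 and 19 on access, and Sections 9 and 20 on the timing of data collection, do not fit together as written.

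**What to change.** **1. Masking and concealment.** Send the computer allocation to the pharmacy only, and have the pharmacy alone dispense. Have an existing co-investigator, who did not dispense and cannot see the therapy field, grade follicles and other signs before any side-effect questions are asked. Name who may know the arm in order to apply the safety rules of Sections 11 and 12, and keep that person from grading. Reconcile the access statements in Sections 10 and 19. State whether the two products can be made indistinguishable; if they cannot, report that the symptom component remains exposed.

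*Cost:* protocol wording, a changed dispensing route, and scheduling effort to have such a grader at each of the three weekly visits.

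**2. PCR as a supportive secondary.** Prespecify PCR-negative at Day 7 (±1 day, swab nearest Day 7) among randomised patients PCR-positive at Day 0, tested only after a significant primary. Label swabs without the arm, and add PCR results to the Section 10 data list. Keep collecting the planned swabs after treatment stops where the patient agrees, and square this with the Section 11 wording on ending participation. Report missing swabs by arm and reason. Show results both with missing counted as not negative and with observed swabs only. State power under equal and unequal loss.

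*Cost:* none in added swabs if the planned schedule is kept; power may be modest if swabs are lost.

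**3. Schedule.** Reconcile the daily to every-other-day swabs of Section 9 with the weekly-only data collection of Section 20.

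### Participation ends after a reaction attributed to the device, with no further outcome collection stated, unlike other exits; the arm comparison may be biased, with direction and size unknown (minor)

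*Combined protocol and SAP*

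**What the plan says.** Two sentences govern patients whose complaint is put down to the product. Section 11: "If there are noted adverse reactions to the device, participation in the study will be terminated for that individual patient." Section 12: "Patients will be withdrawn from the study if the physician deems their symptoms to be clinically related to administration of the device." They agree with each other. Both end study participation, and neither says what happens to later outcomes.

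The other two exits are treated differently in Section 12. For patients who leave by choice: "Patients may withdraw voluntarily from the study at any time, but will be continued to be followed for the duration of the study." For patients who do not use the product: "Non-compliant patients (those who do not take the study device) will be allowed to continue in their respective groups", for the duration of the study.

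Outcomes come from weekly visits (Section 9): "Patients will return once every week for 3 weeks duration in order to assess for resolution of follicular conjunctivitis and symptomatic relief." Safety is checked at the same visits: "Patients will be questioned about adverse effect to treatment each visit and be assessed for surrounding periorbital dermatitis." In Section 11 the co-investigators "will assess patients at each of the follow-up visits for any side effects (listed in the informed consent) to the assigned medical treatment", while the study-level stop applies if "greater than 20% of patients are observed to have an adverse reaction to the spray".

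Section 13 foresees no risk with artificial tears and reports no ocular side effects of Avenova. No section defines an analysis set, an intention-to-treat rule or a method for missing outcomes.

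**The concern.** The plan spells out continued follow-up for voluntary withdrawal, and implies it for non-compliance. It omits it for the one exit that is tied to a suspected effect of treatment. That exit happens after randomisation.

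It may also be more common in one arm. The triggers speak of the device and the spray. Section 22 uses the word device for the product that the manufacturer supplies, and no risk is foreseen in the control arm.

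Removal could be related to outcome. The primary endpoint in Section 8 includes symptomatic improvement, and symptoms judged to come from the product may overlap with those of the infection. It could equally be unrelated: the one reaction named for active assessment is a dermatitis around the eye. The documents do not settle which.

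At stake are the comparability of the patients who remain, and the later safety assessments of the very patients who reacted.

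**Working it through.** **Inputs from the protocol.** Resolution is 20% without treatment (at 7 days) and 50% with it, 39 per group, 80% power (Section 10). Total enrolment is 125 (Section 5).

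**Assumptions.** Two-sided 5% test, that is 2.5% in each direction (no alpha is stated). 1:1 allocation, so 125/2 gives about 62 per arm. Removal in the Avenova arm only. Removed patients left out. Share removed 2% or 5%, because the documents give no reaction rate.

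**The plan's own figure.** With pooled variance and mean rate 0.35:

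n = [1.960·√(2·0.35·0.65) + 0.842·√(0.2·0.8 + 0.5·0.5)]² / 0.30² = (1.322 + 0.539)² / 0.09 = 38.5, so 39 per group. The stated size reproduces and is not disputed.

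**Possible shift in the estimate.** If a share w of the Avenova arm is removed and would have resolved at rate q, the remaining patients show (p − wq)/(1 − w). With p = 50% and w = 5%:
- q = 0: 0.50/0.95 = 52.6%, a difference from control of 32.6 points
- q = 100%: (0.50 − 0.05)/0.95 = 47.4%, a difference of 27.4 points

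The true difference is 30 points. The bias is zero only when q equals the arm's own rate.

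**Error rates with no true effect.** Both arms resolve at 20%. Let a be the removal probability for Avenova non-resolvers and b that for Avenova resolvers, with 0.8a + 0.2b equal to the share removed. The expected observed Avenova rate is 0.2(1 − b)/[0.2(1 − b) + 0.8(1 − a)]. Rates come from simulation with a pooled z-test (1,000,000 trials per setting) and repeat to within about 0.1 point.

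| 5% of Avenova removed | a | b | Expected observed Avenova rate | Error rate favouring Avenova, 39 / 62 per arm |
|---|---|---|---|---|
| None removed (reference) | 0 | 0 | 20.0% | 2.5% / 2.4% |
| Non-resolvers at twice the rate | 0.0556 | 0.0278 | 20.5% | 2.9% / 3.0% |
| Unrelated to outcome | 0.05 | 0.05 | 20.0% | 2.6% / 2.6% |
| Resolvers at twice the rate | 0.0417 | 0.0833 | 19.3% | 2.1% / 2.1% |
| All removed are non-resolvers | 0.0625 | 0 | 21.1% | 3.3% / 3.6% |
| All removed are resolvers | 0 | 0.25 | 15.8% | 0.8% / 0.6% |

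The rate against Avenova is 2.9% / 3.1% when resolvers are removed at twice the rate, and 6.7% / 8.6% when all removed are resolvers. So the largest distortion in this illustration goes against Avenova.

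With 2% removed, the rates favouring Avenova are 2.7% / 2.7% (non-resolvers at twice the rate), 2.5% / 2.6% (unrelated) and 2.4% / 2.3% (resolvers at twice the rate). If both arms lose 5% in the all-non-resolver pattern, the rate is 2.5% / 2.5%.

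**Power at 50% v 20%.** About 81% / 95% with everyone followed, and 80 to 81% / 94% if 5% of Avenova outcomes are lost at random. Lost precision is not the issue.

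**The case against.** The strongest reply is about weight. The protocol expects hardly any reactions, and 5% means about 2 of 39 or 3 of 62 patients. In the intermediate cases a nominal 2.5% moves only to between 2.1% and 3.1%. Part of that comes from the discreteness of the test: at 62 per arm the rate favouring Avenova rises from 2.4% to 2.6% when removal is unrelated to outcome. Only about 0.4 of the 0.6-point rise to 3.0% therefore reflects selective removal. This stands, and it is why the point is minor.

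The bias also presupposes an analysis of observed cases, which the plan does not specify. Counting removed patients as unresolved would give a different result. This stands too, but outcomes never collected cannot be recovered by any later choice of method.

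Uneven removal is an inference. Section 12's non-compliance sentence uses study device in a way that can cover both arms, and side effects are assessed whatever the assigned treatment. Hence possibly, not certainly, more often in the Avenova arm.

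Section 11 opens with a weekly schedule for all subjects, and silence is not a prohibition. But that schedule is not said to survive termination, and ending participation or withdrawing from the study points the other way. At best the text is ambiguous.

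Finally, a reaction first noted at the week-1 visit need not cost the 7-day outcome used in the power analysis. The assessments at weeks 2 and 3 would remain at risk.

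**Conclusion.** The point holds as a minor one. The protocol ends participation after a device-attributed reaction or symptoms without stating further outcome collection, and treats its other exits differently. A comparison of the remaining patients may be biased. Neither the direction nor the size can be derived from the documents, and the effect is probably small if reactions are rare. The figures above are illustrations that rest on an assumed removal share, removal in one arm and an observed-case analysis.

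Three stronger readings are tempting and not supported:
- **The rule favours Avenova.** That would need removed patients to resolve less often than the rest of their arm, which nothing in the documents shows.
- **Only Avenova patients can be removed.** The wording leans that way but does not settle it.
- **Later outcomes are certainly lost, or follow-up is forbidden.** The text states no further collection; it does not rule it out.

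**What to change.** In Sections 11 and 12, separate stopping the assigned product from ending study participation. Then state, for both arms, that a patient withdrawn because of a reaction or symptoms attributed to the assigned treatment continues the weekly outcome and safety assessments already scheduled, unless consent is withdrawn, and is analysed in the randomised group. This extends to these patients the follow-up that Section 12 already gives to voluntary withdrawals.

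One point needs care. Stopping the device after a reaction is at present only implied by the end of participation. If participation continues, that implication disappears unless it is written down, so the passages must be reconciled to keep it explicit. No clinical stopping rule is proposed here. How to handle outcomes that are still missing is a separate choice.

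The cost is one or two sentences and a few visits that are already planned. No power is lost. The Avenova result may look slightly less or slightly more favourable than it would among the remaining patients only.
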